9.3.4. Primary outcome analyses

The outcome population will be used for all outcome analyses. The primary outcome analysis will assess cumulative outcome on the Hopkins Verbal Learning Test (the primary outcome variable) after multiple injections.

Secondary outcome analyses will examine additional outcomes and time points. Five categories of measurements related to outcome will be examined:

- Neuropsychological testing
- Brain MRI results
- Clinical signs and symptoms of cognitive decline
- Biochemical results

9.3.4.1. Primary outcome variable and analysis

The mean change from baseline for the Hopkins Verbal Learning Test will be presented over time. Changes will be analyzed through the 5-year study period. Summary statistics of mean changes, standard deviations, and 95% confidence intervals will be presented.

9.3.4.2. Secondary outcome variables and analyses

9.3.4.2.1. Neuropsychological testing

Other neuropsychological measures such as IQ will be analyzed using the same method as described for the primary analysis.

9.3.4.2.2. Brain MRI

Brain MRI data will be analyzed in three data sets:

- White matter changes and Virchow-Robin spaces will be assessed using the methodology in Matheus et al. 2004, see Appendix C. Absolute and percent change from the month 0 visit to the final study visit in each of the MRI scores will be calculated for each subject. Summary statistics of means, standard deviations, and 95% confidence intervals will be presented.
- Volumes: Whole brain, white matter, gray matter, hippocampal, caudate and ventricular volumes will be calculated. Absolute and percent change from the month 0 visit to the final study visit in each of the MRI scores will be calculated for each subject. Summary statistics of means, standard deviations, and 95% confidence intervals will be presented.
- Diffusion Tensor Imaging and Tractography: Fractional anisotropy values will be used to evaluate white matter structure and function. These variables will be analyzed using the same method as the MRI volume data above.

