The study will be conducted at the Los Angeles Biomedical Research Institute at Harbor-UCLA (LAB-HUCLA), Children's Hospital Oakland Research Institute

(CHORI) and the University of Minnesota (UMN). Additional study sites may be added as subjects are identified. Specific details are below:

- Recruitment: Subjects will be recruited from participants in the MIRC-002 study at LAB-HUCLA and CHORI.
- Procedures: Procedures will be performed at LAB-HUCLA, CHORI, and additional study sites that are added as subjects are recruited to the study. The addition of any new study site will be contingent upon approval by their local institutional review board (IRB), and the IRB at LAB-HUCLA. Neuropsychological testing will be performed at UMN.
- Regulations: The IRBs at CHORI and UMN will oversee the research at these respective sites, with LAB-HUCLA the primary site responsible.

4. Resources Available to Conduct the Human Research

Since subjects will be recruited from among participants enrolled in the pilot (MIRC-002) study:

- All participants are accessible for recruitment
- 67% are anticipated to be enrolled in the proposed study
- Study staff have previously been involved with participants and their families through the pilot study, so are familiar with local culture and attitudes toward clinical research.

Time requirement for the Principal Investigator to conduct and complete the proposed study within the agreed trial period is projected to be 8 hours per week.

Site study staff at the LAB-HUCLA include six members: two co-Primary Investigators, two pharmacists, one Study Coordinator, and one laboratory staff. Study staff at the CHORI site include three members: one site PI, one pharmacist and one study coordinator. Study staff at the UMN include two members: one site PI and one study coordinator. All study staff have completed appropriate training regarding protection of human research subjects, Good Clinical Practices, and HIPAA, and have previously participated in other clinical research trials.

Inpatient study treatments are conducted at the hospital in an area designated for clinical research and study evaluations are completed in separate outpatient clinical research facilities. Principal Investigators have hospital privileges at their respective sites and non-study staff resources are available at each hospital should study participants require medical or psychological support as a result of an anticipated consequence of the research study.

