9.1. Overview

This study will evaluate changes in neuropsychological, radiological, clinical, biochemical measures, and safety after 5 years of intrathecal injections of rhIDU in six MPS-I subjects. The statistical goal is estimation of the magnitude of these changes and their heterogeneity and calculation of rates of adverse events.

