9.2. Study Size

A study size analysis was done for the pilot study. As this study is only open to subjects that have completed the pilot study, the maximum number of subjects available for this study is six.

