9.3. Data analysis methods

A descriptive summary of subject characteristics at baseline will be made with frequencies and percentages for categorical variables, and with mean and standard deviation or median and quartiles, depending on statistical distribution, and range for continuous measurements. Some analyses specified below require that continuous observed or derived measures have statistical properties such as normal distributions. If there is evidence that statistical requirements are not met, transformations to achieve those requirements will be performed. If such transformations are not possible, non-parametric analogues to the proposed parametric methods will be substituted.

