9.3.3.1. Laboratory evaluations: CSF and anti-IDU antibody

Absolute, percent, and reference range change in CSF glucose, protein, and cell counts from the month 0 visit to the subsequent month visits will be calculated for each subject, and summarized over subjects with means, standard deviations, and 95% confidence intervals. Frequency and percent of subjects with values outside their reference range will be reported.

Absolute and percent change ELISA anti-IDU antibody from the month 0 visit to the subsequent month visits will be calculated for each subject, and summarized over subjects with means, standard deviations, and 95% confidence intervals. Frequency and percent of subjects with values outside their reference range for the subject's age will be calculated.

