APPENDIX C

MRI of brain: Scoring system

Abnormal signal intensity:

Lesions will be estimated as to size (3 dimensions) and number, and will be divided by location into basal ganglia, white matter, and cortex. Signal changes observed on T2 images will be graded on a scale from 0-3, where 0 is absent, 1 is patchy and confined to the periventricular area, 2 is patchy but in other white matter areas as well as periventricular, and 3 is diffuse.

Enlargement of perivascular space:

Enlargement of the perivascular space will be classified in five brain regions: periventricular and subcortical white matter, corpus callosum, basal ganglia, thalamus, and brainstem. These regions will be scored for enlargement on a scale from 0-3, where 0 is no enlargement, 1 is < 3mm enlargement, 2 is between 3 and 8 mm enlargement, and 3 is > 8 mm of enlargement.

Other findings, such as brain atrophy and megacisterna magna will be graded on a scale from 0-3, with 0 as absent, 1 as mild, 2 as moderate, and 3 as severe. Additional abnormalities will also be noted.

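### Percent change is required for 0–3 MRI grades and CSF cell counts, where a starting value of 0 leaves it undefined and no rule says what to do

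*Combined protocol and SAP*

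**What the plan says.** **MRI grades.** The first bullet of section 9.3.4.2.2 covers white matter changes and Virchow-Robin spaces scored by Appendix C. For each subject it requires "Absolute and percent change from the month 0 visit to the final study visit in each of the MRI scores", summarized by means, standard deviations and 95% confidence intervals. The second bullet uses the same words for brain volumes; this point does not concern volumes. Appendix C says of white matter signal: "Signal changes observed on T2 images will be graded on a scale from 0-3, where 0 is absent". Of the five perivascular regions it says: "These regions will be scored for enlargement on a scale from 0-3, where 0 is no enlargement". That makes at least six grades per subject on which 0 is an ordinary value.

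**CSF.** Section 9.3.3.1 requires "Absolute, percent, and reference range change in CSF glucose, protein, and cell counts" from month 0 to later visits, with the same summaries and a count of subjects outside the reference range. It also requires absolute and percent change in anti-IDU antibody.

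**General fallback.** Section 9.3 says: "If there is evidence that statistical requirements are not met, transformations to achieve those requirements will be performed". If that is not possible, non-parametric analogues are used.

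**Size and goal.** Section 9.2 says that "the maximum number of subjects available for this study is six", and section 4 that "67% are anticipated to be enrolled in the proposed study". Section 9.1 says: "The statistical goal is estimation of the magnitude of these changes and their heterogeneity".

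**Subjective score.** In 7.7.3.5 the subject confirms four listed symptoms at baseline, may add others, and at each later visit rates each from -3 to +3. Section 9.3.4.2.3 forms a total from day 0 to the final visit, as a mean over at most five areas of the summed ratings, then gives mean, SD and 95% CI. Section 7.8.2.3.4 treats the same data as qualitative.

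**The concern.** A per-subject quantity that is to be averaged must exist for every subject. Here it does not exist for anyone who starts at 0, and on these scales 0 is the normal finding. The analyst would have to choose a rule after seeing the data of at most six subjects. One obvious choice, leaving out zero starts, is selective: it removes the subjects in whom an abnormality first appears during the study. The mean absolute change and the mean percent change could then describe different people while appearing side by side.

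The subjective total raises a smaller question of the same kind: whether the number reflects the subject's course or merely how many visits were made.

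**Working it through.** The plan states no figure to reproduce here, so the check is whether the rule can be applied and what follows if it cannot.

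**1. The formula.** Percent change = 100 × (final − start)/start. Of the 16 start/final pairs on a 0–3 grade, the four with start 0 have no value. Where it is defined, it depends on the start: one grade worse is 100 × (2 − 1)/1 = +100% from grade 1, and 100 × (3 − 2)/2 = +50% from grade 2.

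**2. Does section 9.3 help?** A transformation needs a value to transform. A non-parametric method needs values to order, and a subject going from 0 to 0 gives 0/0. Calling that no change would be reasonable, but it would be a rule the plan does not contain. By contrast, the FIM total runs from 13 to 91 (Appendix B), so its percent change always exists.

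**3. How few subjects, if zero starts are left out.** The share q starting at 0 is assumed, with subjects independent. The number contributing is binomial (N, 1 − q), and P(at most one) = q^N + N(1 − q)q^(N−1). N is six (section 9.2) or four (0.67 × 6 = 4.02, section 4). For example, with N = 6 and q = 0.5: 1/64 + 6/64 = 0.109.

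| Assumed q | 25% | 50% | 75% |
|---|---|---|---|
| Mean contributing, of six | 4.5 | 3 | 1.5 |
| P(at most one), of six | 0.5% | 11% | 53% |
| Mean contributing, of four | 3 | 2 | 1 |
| P(at most one), of four | 5% | 31% | 74% |

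With one contributor there is no SD or interval. With more, the 95% half-width is t(0.975, n − 1)/√n SDs: 1.05 for n = 6, 1.59 for n = 4, 2.48 for n = 3 and 8.98 for n = 2.

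**4. How much the choice of rule matters.** Invented grades in one region: starts 0, 0, 1, 1, 2, 2; finals 1, 2, 1, 1, 2, 1.
- Absolute changes are 1, 2, 0, 0, 0, −1: mean 2/6 = +0.33, SD 1.03, 95% CI 0.33 ± 1.05 × 1.03, about −0.75 to 1.42 (n = 6).
- Percent change without zero starts: 0, 0, 0, −50. Mean −12.5%, SD 25, 95% CI −12.5 ± 1.59 × 25, about −52% to 27% (n = 4).
- Percent change with the zero denominator replaced by 1: (100 + 200 − 50)/6 = +42%. Replaced by 0.5: (200 + 400 − 50)/6 = +92%. Replaced by 0.1: (1000 + 2000 − 50)/6 = +492%.

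The two subjects with a new abnormality are absent from the second line, and they dominate the third.

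**5. Subjective total.** Three-monthly visits over five years give 60/3 = 20 scorings after Visit 1 (21 if Visit 1 is scored). Suppose ratings are against baseline and are summed over visits. A subject who becomes slightly better once and stays so scores 20 × 1 = 20 in that area. Take six subjects at a constant +1, one of whom leaves after five scorings: totals 20, 20, 20, 20, 20, 5. Mean 105/6 = 17.5, SD √(187.5/5) = 6.1, half-width 2.571 × 6.12/√6 = 6.4, 95% CI 11.1 to 23.9. All six report the same course; the spread comes only from length of follow-up.

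**The case against.** **A usable summary already exists.** Absolute change is planned for the same MRI grades. For CSF, absolute change, reference-range change and out-of-range counts are all planned. This stands, and it is why the point is minor.

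**Nothing shows that zero starts will be common.** This also stands. The documents give no starting grades or cell counts. The large probabilities in the table come from the 75% assumption; at 25% with six subjects the figure is 0.5%.

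**Section 9.3 may be broader than normality.** It covers derived measures and names normal distributions only as an example. Even read broadly, it gives no value for a change from 0 to 0.

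**Dependence on the starting grade is simply what relative change means.** Agreed; that alone is not an error.

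**A reader might infer that zero-start subjects necessarily drop out, or that percent change would reverse the finding.** The documents support neither. Exclusion is one choice among several, and in the invented example both intervals include 0.

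**A reader might also infer that the subjective total is wholly undefined.** That goes too far. The span from day 0 to the final visit favors summing over visits and averaging over areas. Baseline is the only reference point named in 7.7.3.5. Four symptoms plus one added category can make up to five areas. The Study Operations Manual cited in 7.2, not available here, may state the comparator. What survives is the recounting under that natural reading, and the conflict with 7.8.2.3.4.

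**Conclusion.** Wrong as written, and minor. That percent change does not exist from a zero start, and that the plan supplies no rule, needs no assumption. The numbers of subjects left depend on an assumed share of zero starts and on the analyst choosing exclusion. The worked grades are hypothetical and show only that the answer turns on an unstated choice.

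The subjective-score point is lesser and conditional: it holds if ratings are against baseline and summed over visits, which the text favors but does not state. The mismatch between qualitative data in 7.8.2.3.4 and means, SDs and intervals in 9.3.4.2.3 is on the page.

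Only secondary and safety descriptive summaries are affected. The primary Hopkins analysis (9.3.4.1) uses change without percent and is unaffected.

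**What to change.** - In 9.3.4.2.2 (first bullet) and 9.3.3.1, delete percent change for the 0–3 MRI grades and for CSF cell counts. Rely on the absolute change already planned and, for CSF, on reference-range change.
- If percent change is kept, limit it to subjects with a non-zero start, and report that n and the number who went from 0 to above 0. Apply the same rule to anti-IDU antibody if a zero or undetectable start is possible.
- Keep percent change for volumes, fractional anisotropy, CSF glucose and CSF protein.
- In 7.7.3.5, state the comparator actually used. If it is baseline, replace the sum in 9.3.4.2.3 with the final-visit score averaged over the areas scored, and show per-visit means with n. If it is the previous visit, the sum over visits can stay.
- Reconcile 7.8.2.3.4 with 9.3.4.2.3.

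The cost is wording in a few sections and no new data. Relative change in grades and cell counts would no longer be reported. A final-visit score still mixes early leavers with five-year completers, which is the reason for the per-visit means. Ratings whose comparator was not recorded cannot be converted and should be flagged.

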9.3.4.2.3. Clinical signs and symptoms of cognitive decline

Absolute and percent change from the month 0 visit to final study visit in (1) the MMSE, (2) the six-minute walk test, and (3) the FIM scale will be calculated for each subject, and summarized by presenting means, standard deviations, and 95% confidence intervals.

Each subject's total subjective improvement score from the day 0 visit to the final study visit will be calculated as the mean (of up to the five clinical areas) of the sum of all the subjective scores. These changes will be summarized by presenting means, standard deviations, and 95% confidence intervals.

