6.4. Study Timelines

The duration of each subject's participation in the study is expected to be five years. We anticipate enrolling these subjects over a 4-year period. The estimated date of completion of the study is 10 years following the onset of the study.

7. Procedures Involved in the Human Research

This study is a five-year open-label, prospective trial in 6 MPS I subjects age six years or greater who have completed a 24-month open label study (MIRC-002). Potentially eligible subjects who (or, if appropriate whose parents or guardians) have provided signed, written informed consent will first participate in a baseline screening phase. This will occur at least six months after subjects have completed the MIRC002 pilot study. During baseline screening, the subjects will receive the baseline evaluations outlined below, and their eligibility will be determined. Every three months, subjects will receive intrathecal recombinant human α-L-iduronidase (IT rhIDU) approved as Aldurazyme® [laronidase] for the treatment of cognitive impairment in patients with mucopolysaccharidosis I (MPS I). Neuropsychological testing and MRI will be performed at baseline and at one year intervals. Safety will be monitored continuously throughout the subject's study participation through recording all adverse events (AEs) and periodically performing clinical and laboratory evaluations.

Study subjects will receive intrathecal enzyme therapy only during the study; intrathecal enzyme therapy will not be administered at the end of the five-year period. If further intrathecal enzyme is desired, the subject may enroll in further intrathecal research if another study is available.

To assure that subjects enrolling in the trial have maximum access to alternative therapy, subjects will be asked to receive counseling regarding other available appropriate medical and surgical alternatives prior to enrollment in this trial.

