7.2. Schedule of Study Evaluations

After obtaining informed consent, the investigator will conduct the study as outlined in the following sections. Table 1 summarizes the nature of the assessments and treatments and their timelines. Refer to Study Operations Manual for guidelines regarding test assessments and procedures for handling/shipment of all central laboratory samples.

Table 1 Schedule of study assessments and treatments

Month Number	Baseline	Visit 1/Odd Numbered Visits	Visit 2/Even Numbered Visits	End Study
Neuropsychological testing	X		yearly	
MRI of brain	X		yearly	
Clinical tests				
History and Physical examination	X	X	X	X
Neurologic examination	X	X	X	X
Photography and video (optional)	X	X	X	X
Six-minute walk test	X	X	X	X
Subjective response of clinical symptoms	X	X	X	X
FIM scoring	X	X	X	X

Laboratory tests (CSF)				
Protein, glucose, cell count		X	X	
GAG levels		X	X	
Anti-rhIDU antibody		X	X	
CSF iduronidase assay		X	X	
Laboratory tests (blood)				
Anti-rhIDU antibody	X	X	X	X
CBC, Chem panel 20, Coagulation studies	X	X	X	X
Neurophysiologic test				
CSF flow study	X			
Investigator Global Assessment				
	X	X	X	X
Treatments				
Intrathecal rhIDU		X	X	

Visits occur at three-month intervals starting from Visit One. There may be a variable period between Baseline/Screening and Visit One from five days to three months. If the period between Baseline/Screening and Visit One is less than one week, then all of the other assessments do not need to be repeated for Visit One.

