7.7.3.5. Subjective response of clinical symptoms

The subject will be asked at baseline to verify if they have the following symptoms: headache, memory loss, difficulty concentrating, decreased ability to function at work or school or in their daily life. Also, the subject may identify additional CNS symptoms that concern them. At each subsequent visit, the symptoms should be scored by the subject as no change (score 0), slightly better (+1), moderately better (+2), much better (+3), slightly worse (-1), moderately worse (-2) or much worse (-3).

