7.8.2.3.4. Subjective improvement

Subjective accounts will be recorded and kept as qualitative data.

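### The subjective improvement score sums ratings over visits without naming what each rating is compared with; if that is baseline, the score depends on how many visits were scored

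*Combined protocol and SAP*

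**What the plan says.** Section 7.7.3.5 has the subject confirm at baseline which of four symptoms are present ("headache, memory loss, difficulty concentrating, decreased ability to function at work or school or in their daily life") and lets the subject add other CNS symptoms. It then says: "At each subsequent visit, the symptoms should be scored by the subject as no change (score 0), slightly better (+1", with the scale running on to +3 and down to −3. It names no visit against which better or worse is judged.

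Table 1 in Section 7.2 schedules this assessment at baseline, at every treatment visit and at End Study. "Visits occur at three-month intervals starting from Visit One", and Section 7 opens with: "This study is a five-year open-label, prospective trial in 6 MPS I subjects".

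Section 9.3.4.2.3 defines the "total subjective improvement score from the day 0 visit to the final study visit" as "the mean (of up to the five clinical areas) of the sum of all the subjective scores". The result is summarised over subjects with means, standard deviations and 95% confidence intervals. Section 7.8.2.3.4, the endpoint entry, says only: "Subjective accounts will be recorded and kept as qualitative data".

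**The concern.** The mean in the definition is taken over symptom areas, so the natural reading is that the sum runs over visits. Nothing divides by the number of visits, fixes a common number, or deals with missed visits.

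Unequal visit counts are foreseeable. The outcome population (Section 9.3.1) needs only one dose and one post-baseline measurement. Section 14.2 stops evaluations after withdrawal unless an ongoing adverse event calls for them. Section 14.1 lists a wish for another treatment for cognitive decline as a reason for removal, so leaving may be related to the outcome being rated.

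If each rating is against baseline, the same lasting benefit is counted again at every visit, and the reported mean and interval mix symptom change with length of follow-up. With at most six subjects, one or two early leavers could dominate the summary.

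**Working it through.** The plan gives no figure for this score, so there is none to reproduce. The check is arithmetic on the definition.

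**Inputs.** Ratings run from −3 to +3 at each visit after baseline (Section 7.7.3.5). Visits are three-monthly (Section 7.2) for five years in six subjects (Section 7), so about 5 × 4 = 20 scored visits; 20 to 22 depending on how Visit 1 and End Study are counted. The illustrative subjects below are assumptions: each gives the same rating in every area at every visit attended.

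**Reading A: each rating is against baseline.** Score = mean over areas of the sum over visits = (scored visits) × (average rating).

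1. Possible range: 20 × (±3) = ±60 for a completer (±63 or ±66 with 21 or 22 visits), 8 × (±3) = ±24 for a subject with 8 visits, and 4 × (±3) = ±12 for one who leaves at a year.
2. Order: +1 at 20 visits gives 20; +3 at 6 visits gives 18. The less improved subject scores higher, and this holds for any constant +3 subject with 6 or fewer visits.
3. Spread: six subjects all at +1 with 20, 20, 20, 20, 8 and 4 visits have scores equal to those counts. The mean is 92/6 = 15.3 and the SD 7.3; the 95% interval (t, 5 df) is 7.6 to 23.0. Every average rating is +1, so all of the spread is follow-up. With 20 visits each, the mean is 20 and the SD 0.
4. Sign: three completers at +1 score 20 each; three subjects at −3 who leave after 4 visits score −12 each. The mean score is (3 × 20 − 3 × 12)/6 = +4. The subjects' average rating is (3 × 1 − 3 × 3)/6 = −1. A net decline would be summarised as improvement.
5. Direction: fewer visits move the total toward zero. That lowers it for an improver and raises it for a decliner.

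**Reading B: each rating is against the previous visit.** The sum is then net change since day 0. A single +1 followed by no change totals 1, whether the subject is seen 4 or 20 times. A missed visit can still lose an increment, but time in study no longer inflates the total.

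**Comparing the readings.** A lasting one-step benefit scores 20 under A and 1 under B. Baseline is the only visit that Section 7.7.3.5 names before the ratings, and Section 7.7.6 states baseline as the reference for the parallel investigator scale. That favours A without settling it.

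**Effect of removing the sum under A.** Dividing by scored visits, or using the final-visit score alone, returns the score to −3 to +3. In these constant-rating examples, a +1 subject then scores 1 after 4 visits or 20.

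**The case against.** The strongest reply is that the comparator is unstated, and that Section 9.3.4.2.3 calls the result a total from day 0 and treats it as a change, which fits previous-visit ratings. The authors also wrote a baseline comparator for the investigator scale when they wanted one. This stands, and it makes the concern conditional. A reader might infer that the score necessarily measures time in study; the documents do not support that without the baseline assumption.

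A second reading is that the sum runs over areas at a single visit and is divided by their number. It is less natural for a total of all scores from day 0 to the final visit, but it is not excluded.

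A reader might also infer that withdrawal always lowers the score. It does so only when ratings are positive; for a worsening subject it raises the score.

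Two textual points look like contradictions but are only loose wording. Five areas is compatible with four listed symptoms plus one added by the subject, although no cap on additions is stated. The qualitative data in Section 7.8.2.3.4 can be narrative accounts, since Section 8 separately lists numeric subjective improvement scores among the stored data.

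Finally, no test or decision uses this score, and Section 9.3.2 summarises duration of enrollment separately. Unequal follow-up would therefore be visible, though not adjusted for.

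**Conclusion.** The concern holds in conditional form. Two things are certain: the reference visit is not stated, and the sum carries no adjustment for the number of visits scored. If ratings are against baseline, the score is visits times average rating, and unequal attendance can distort its size, spread and even sign, as the working shows. If ratings are against the previous visit, the sum is a legitimate net change and only missed increments remain a problem.

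The distortion also requires unequal visit counts; if all subjects attend the same visits, the sum is only a rescaled mean. The visit patterns and constant ratings are illustrations, not forecasts. This is one descriptive secondary measure, and the Hopkins Verbal Learning Test analysis is untouched. The correction is worth making because the stated rule can give a misleading summary and is cheap to repair.

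**What to change.** 1. Confirm from the case report form which visit subjects were asked to compare with, and state it in Section 7.7.3.5. Do not assume baseline: ratings already collected under another instruction cannot be redefined in the analysis section.
2. If the reference is baseline, replace the sum in Section 9.3.4.2.3 with the final-visit score averaged over the areas identified at baseline. This matches the month 0 to final visit convention of the other measures in that section. Add the mean score per attended visit as support, and say which visit counts as final for a subject who leaves early.
3. If the reference is the previous visit, keep the sum and describe it as net change. Report the number of scored and missed visits with each total. Do not use the final-visit score alone, because it would discard all change before the last interval.
4. As tidying, state how many subject-added areas count toward the five, and distinguish the narrative accounts in Section 7.8.2.3.4 from the numeric scores in Sections 8 and 9.3.4.2.3.

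The cost is a few sentences across three or four sections and one check of the form, with no new data. The downside under step 2 is that a final-visit score uses fewer ratings; the supporting per-visit mean offsets this.
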